**Methods/Procedures:**

This is a prospective, randomized study with outcomes determined by blinded event adjudication (PROBE). Patients will be screened upon admission to the hospital, and enrolled within 24 hours from admission. Subjects will then be randomized to either the surveillance arm or the no surveillance arm. Subjects enrolled in the surveillance arm will undergo bilateral DUS on post-injury days 1, 3, 7, and every 7 days thereafter until discharge from the hospital. Subjects in the no surveillance arm will have routine hospital care on the trauma service, with no DUS performed unless symptomatic for DVT. (See Appendix B) Trauma physicians and advanced practice clinicians (APCs) will perform daily history and physical examinations targeted at eliciting symptoms and signs of potential VTE in all subjects.

All subjects enrolled in both arms of the study will have appropriate VTE prophylaxis provided (enoxaparin 30mg SQ every 12 hours if BMI<30, enoxaparin 0.5mg/kg SQ every 12 hours if BMI>30) according to the current IMC trauma service guidelines. VTE chemoprophylaxis will be started upon admission, or when deemed clinically safe according to the trauma service protocols. If chemoprophylaxis is not begun right away (because of solid organ injury, traumatic brain injury, etc.), those subjects will receive mechanical prophylaxis according to the trauma service guidelines.

Asymptomatic DVT in the surveillance group will be determined on the day of the DUS, prior to hospital discharge. Symptomatic DVT and PE during hospitalization in both groups will be pursued using the Wells score as guidance for DVT diagnosis and using objective imaging as diagnostic confirmation. 90 day follow-up of all subjects will be performed by reviewing medical records in the Intermountain Healthcare computerized medical record to look for evidence of VTE. All outcomes will be adjudicated by a panel of independent physician adjudicators blinded as to whether the patients were randomized to surveillance or not.

All subjects diagnosed with acute proximal DVT or PE will be treated with therapeutic doses of anticoagulants while in the hospital and after discharge, as appropriate. Subjects who are diagnosed with isolated calf DVT while in the hospital will have a follow up DUS on day 14 after

the initial diagnosis to check for thrombus propagation, per current ACCP guidelines. Patients in whom thrombus propagates to the proximal deep veins will receive therapeutic anticoagulation unless contraindicated, according to the usual standard of care. See Appendix B for a flow chart that depicts treatment decisions throughout the study.

In order to investigate our hypothesis, this study will compare outcome variables between the surveillance and the non-surveillance groups.

**Randomization:**

Randomization will be performed by the randomization module in the REDcap system. Subjects will be randomized to either the screening group or a non-screening group.

**Informed Consent:**

Potential subjects will be approached by the investigators or by authorized members of the study team in the ICU. They will be given a form that briefly explains the study and, if they desire, by signing at the bottom of the form, they may opt out of the study. Patients will be given as much time to consider participation as they need and they will be able to ask questions about the study.

**Risks:**

Participation in this study poses minimal risks. There are no risks associated with the duplex ultrasound procedure.

**Benefits:**

We do not know if this study will directly benefit subjects. Most DVT that we diagnose is clinically silent and is found with DUS imaging. Being evaluated with DUS may benefit subjects if it helps us to see DVT that we would not otherwise know is there, so we can treat it.

The information gained from this research may help future patients and will contribute to knowledge regarding ultrasound surveillance in high risk trauma patients. Answering this research question is important as it may lead to less PE, fewer major bleeding episodes, and less mortality for patients in the future.

**Compensation:**

Subjects will not be compensated.

**Data Collection:**

[figure not shown]
The following variables will be collected for all subjects in both arms of the study in a secure, computerized database (REDcap):

1. Patient demographics
2. Past medical/surgical/family/social history
3. Mechanism of injury
4. Injuries sustained and Injury Severity Score (ISS)
5. All items in the Caprini DVT risk assessment model (See Appendix C)—this information will be used for descriptive purposes and as a means of comparing the two study groups.
6. All items in the Risk Assessment Profile (RAP) for VTE (See Appendix D)—this information will be used for descriptive purposes and as a means of comparing the two study groups.
7. VTE pharmacoprophylaxis agent, dose, time from admission to first dose, interruptions in pharmacoprophylaxis and for what reason
8. Mechanical prophylaxis modality used
9. Asymptomatic DVT in surveillance group with location
10. Symptomatic DVT/PE with location during hospitalization and at 90 days
11. DVT propagation with location during hospitalization and at 14 days
12. Major and clinically relevant bleeding during hospitalization and at 90 days (see Appendix E).
13. All cause mortality during hospitalization and at 90 days

**Data Analysis/Statistics:**

A historic baseline incidence of the composite outcome of major bleeding events plus proximal DVT on the trauma service is about 5.5%. We expect that in the no surveillance group, the incidence of the composite outcome will be higher. We are not entirely sure how much higher, which is one of the reasons for performing this vanguard trial. The below power analysis reflects that. Based on this power analysis, we would need to enroll at least 1000 subjects in each arm to discern a true difference, perhaps more, depending on the difference in events between the two groups. It is unreasonable given current financial and time constraints to do this definitively at a single center.

Based on historical trauma service admissions of 3000 per year, we estimate that 65-75% of admitted patients will qualify for the study, and 50-75% of those will agree to enroll. Thus, we estimate that over the course of one year, we could enroll about 300 patients per arm. This number of patients should be sufficient to help us determine the feasibility of a definitive, likely multi-institutional future trial.

A chi-squared test will be calculated to compare the rate of VTE between the surveillance group and the no surveillance group

Effect Size	Minimum Sample Size per Group
6.5% (+1.0%)	Doesn't achieve 80% power at n=5000 per group
7.0% (+1.5%)	4,200
7.5% (+2.0%)	2,500
8.0% (+2.5%)	1,600
8.5% (+3.0%)	1,200
9.0% (+3.5%)	900
9.5% (+4.0%)	700
10.0% (+4.5%)	600

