In debating the utility of DUS in patients receiving prophylaxis with LMWH, one must acknowledge the emerging evidence questioning the current standard of LWMH dosing. Fixed twice-daily enoxaparin dosing for all patients has been found to result in subtherapeutic anti-Xa levels and thus may not constitute adequate prophylaxis. Data exists suggesting that a one-size-fits-all approach is inferior to a weight-based regimen using enoxaparin for VTE prophylaxis in trauma patients. [10] [11] As illustrated by the conflicting and poor retrospective data cited above, more evidence and prospective data is needed regarding the impact of DUS surveillance in trauma patient outcomes.

When assessing which trauma patients might warrant DUS screening, a risk assessment tool must be applied. The most common risk factors identified in the literature include age, ISS, specific underlying conditions, spinal cord injury, long bone and pelvic fractures. [7] [8] [9] [10] Two validated VTE risk assessment tools exist for hospitalized patients, one by Caprini and one by Maynard and Stein. [12] [13] Neither of these scoring systems, however, have been validated in the trauma patient population.

The risk assessment profile (RAP) score, developed by Greenfield in 1997, [14] has been validated retrospectively in two analyses, and may be more applicable to assessing the trauma patient population. [13] [15]

At IMC, our trauma service has adopted an aggressive VTE prophylaxis protocol that involves risk-stratifying patients upon admission. Currently, only high-risk patients for VTE in whom enoxaparin is contraindicated undergo regularly scheduled bilateral lower extremity DUS as surveillance for DVT. We hypothesize that high-risk trauma patients, regardless of chemoprophylaxis, who undergo scheduled DUS surveillance for lower extremity DVT will have a lower rate of symptomatic DVT, DVT propagation, and symptomatic or fatal pulmonary embolism (PE) than those who do not have screening.

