### **Significance:**

VTE has been deemed a major threat by the US Surgeon General and the Centers for Medicare and Medicaid Services (CMS). Hospitals are under pressure to reduce or even eliminate VTE, or risk financial repercussions. The current ACCP guidelines do not differentiate high-risk trauma patients from lower-risk patients in the recommendations against routine DUS screening. Haut et al. identified significant variability in opinion and protocols among trauma surgeons and hospitals regarding regular screening for DVT, and found that the VTE rate may be more a function of surveillance bias than of the quality of care. [3] At our trauma service at IMC, our DVT rate is currently about 3%, [16] which has been deemed “too high” according to Intermountain

Healthcare and national targets. Most (approximately 85%) of the DVTs that we diagnose are clinically silent and are found during DUS surveillance of high risk patients.

If we were to discontinue routine DUS surveillance of the highest risk trauma patients, our DVT rate would certainly decrease. It is not at all clear, however, that this would translate to better overall patient outcomes, e.g., less PE, less major bleeding episodes, less mortality. It is very important to answer this question in a prospective, randomized fashion, as this has never been done since the advent of LMWH use for chemoprophylaxis.

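### The composite behind the sample-size table (major bleeding plus proximal DVT) matches neither the hypothesis nor the tested outcome, omits PE, and assumes a direction the protocol does not explain

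*Combined protocol and SAP*

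**What the plan says.** The protocol describes its main outcome in three ways.

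- **Hypothesis** (Background and Significance, last paragraph): scanned patients "will have a lower rate of symptomatic DVT, DVT propagation, and symptomatic or fatal pulmonary embolism (PE) than those who do not have screening". Bleeding is not mentioned.
- **Test** (Data Analysis/Statistics): "A chi-squared test will be calculated to compare the rate of VTE between the surveillance group and the no surveillance group". Hypothesis/Research Questions defines VTE as DVT and PE. The test is not limited to symptomatic events.
- **Planning figures** (Data Analysis/Statistics): "A historic baseline incidence of the composite outcome of major bleeding events plus proximal DVT on the trauma service is about 5.5" (per cent). The direction is stated: "We expect that in the no surveillance group, the incidence of the composite outcome will be higher". The table runs from 6.5% to 10.0% without surveillance, and the text concludes that a definitive trial needs at least 1000 per arm. Not knowing how much higher the composite would be is given as one reason for the vanguard.

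Three other statements bear on the direction. The Significance section says: "If we were to discontinue routine DUS surveillance of the highest risk trauma patients, our DVT rate would certainly decrease". It puts the service's DVT rate at about 3% and the silent share of diagnosed DVT at about 85%. Methods/Procedures scans controls only when they have symptoms. It also says: "All subjects diagnosed with acute proximal DVT or PE will be treated with therapeutic doses of anticoagulants".

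**The concern.** The only outcome with a baseline rate and a sample size is one that the hypothesis does not name and the test does not use. It has three weaknesses as a planning outcome.

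1. PE is not a component, so a reduction in PE leaves it unchanged.
2. Proximal DVT is not limited to symptomatic disease. Silent proximal clots are found mainly in the arm that is scanned on schedule, so detection alone raises the composite there.
3. Bleeding is added without a reason. Detection leads to anticoagulation, so bleeding may move in the opposite direction to the clots prevented.

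The Background section itself cites a cost-effectiveness study of twice-weekly scanning that reported more DVT and less PE. On this composite, the extra proximal DVT in such a result would count against surveillance and the avoided PE would count for nothing. At stake are the endpoint, the effect size and the figure of 1000 per arm that the vanguard hands to a definitive trial.

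**Working it through.** **1. The plan's own table.** Inputs: 5.5% against each listed rate, equal arms, 80% power. The power is named only in the first row ("Doesn't achieve 80% power at n=5000 per group") and is taken to apply throughout. Alpha and sidedness are not stated; I assume 0.05, two-sided.

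n = [1.96·√(2·p̄(1−p̄)) + 0.8416·√(p₁(1−p₁) + p₂(1−p₂))]² / (p₂−p₁)²

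For 5.5% against 8.5%, p̄ = 0.07 and n = (1.96 × 0.3608 + 0.8416 × 0.3602)² / 0.03² ≈ 1,135.

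| Rate without surveillance | Stated n | Uncorrected | Continuity-corrected |
|---|---|---|---|
| 7.0% | 4,200 | 4,087 | 4,220 |
| 7.5% | 2,500 | 2,384 | 2,483 |
| 8.0% | 1,600 | 1,580 | 1,659 |
| 8.5% | 1,200 | 1,135 | 1,201 |
| 9.0% | 900 | 861 | 917 |
| 9.5% | 700 | 680 | 729 |
| 10.0% | 600 | 554 | 597 |

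Every stated figure is within 3% of one of the two methods. At 6.5% and 5000 per arm, power is 55.8%, which agrees with that row. The arithmetic is sound; the question is what it counts.

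**2. What each outcome counts.**

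| Event | Hypothesis | Test | Planning composite |
|---|---|---|---|
| Symptomatic proximal DVT | yes | yes | yes |
| Propagation to proximal veins | yes | as DVT | as proximal DVT |
| Silent proximal DVT found by scan | not unless it is propagation | not excluded | not excluded |
| Symptomatic or fatal PE | yes | yes | no |
| Major bleeding | no | no | yes |

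**3. Direction, by illustration.** If none of the silent 85% were found, recorded DVT would go from 3% to 3% × 0.15 = 0.45%. For the composite, let d be the proximal DVT share of the 5.5% and f the fraction of silent clots that later become symptomatic. Neither is given. With bleeding unchanged and no overlap between components:

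rate without surveillance = 5.5% − d × 0.85 × (1 − f)

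- d = 3%, f = 0: 5.5 − 2.55 = 2.95%
- d = 1%, f = 0.5: 5.5 − 0.425 = 5.1%
- f = 1, any d: 5.5%

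To exceed 5.5%, missed clots must produce new proximal DVT, for example by propagation from the calf, or bleeding must be more frequent without scanning.

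**4. What 1000 per arm presupposes.** It lies between the 9.0% row (900) and the 8.5% row (1,200). Power at 1000 per arm is 85.6% and 74.9% respectively, so the figure needs a rise of about 3.0 to 3.5 points. With bleeding unchanged, reaching 8.5% means that proximal DVT becomes (d + 3.0)/d times its present level: 4.0, 2.5 or 2.0 times for d = 1%, 2% or 3%. If the whole recorded 3% became proximal DVT, the composite would be 5.5 − d + 3.0, which is 7.5%, 6.5% or 5.5%. Rows at 8.5% and above therefore need more DVT than is now recorded, or more bleeding.

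**5. Limits of steps 3 and 4.** The 3% is a service-wide figure. According to Background and Significance, only high-risk patients who cannot receive enoxaparin are now scanned. DVT in the trial population may be higher, and for the same reason the 5.5% need not be the rate in a fully scanned arm.

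**The case against.** Several stronger readings are tempting, and the documents do not support them.

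- *The composite cannot show the hypothesised benefit at all.* Too strong. Its proximal DVT part could register fewer symptomatic proximal DVTs and less propagation. Only PE lies wholly outside it, and the hypothesis does not rank PE above the other two.
- *The assumed direction contradicts the Significance section.* Not strictly. That section speaks of all recorded DVT, while the composite is proximal DVT plus bleeding. Propagation of missed clots could raise the composite.
- *The plan itself expects bleeding to rise with scanning.* It does not. The Significance section calls the effect of stopping scans on PE, bleeding and mortality unclear, and Methods/Procedures qualifies treatment with a clause on appropriateness. More bleeding in the scanned arm is a plausible inference only.
- *The vanguard would report a benefit as harm.* No analysis of the composite is planned here. The test is on VTE, PE is collected to 90 days, and 300 per arm is justified by one year's enrolment and feasibility.

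It is also fair to say that one composite of efficacy and harm can be a legitimate net-benefit measure, and that the protocol does not commit the definitive trial to this one. But a net-benefit measure has to count the benefit, and no reason is given for leaving PE out. VTE, the outcome actually tested, has no baseline rate or sample size, so the composite is all the definitive trial would inherit.

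**Conclusion.** The concern holds in limited form. The planning composite differs from both the hypothesis and the tested outcome, cannot register a PE benefit, and depends on how intensively each arm is scanned. Its assumed direction is unexplained rather than shown to be wrong. The size of any shift cannot be derived from the documents: 2.95% to 5.1% against the baseline of 5.5% rests on an assumed proximal share of 1 to 3 points, 85% of it silent, 0% to 50% later becoming symptomatic, and unchanged bleeding. New propagation could reverse it. The table arithmetic and the vanguard's size are unaffected. The endpoint, the effect sizes and the figure of at least 1000 per arm should not be carried forward as they stand.

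**What to change.** In Data Analysis/Statistics:

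1. Name one primary outcome and use it for both the planning figures and the chi-squared test. Build it from events sought in the same way in both arms: symptomatic proximal DVT, including symptomatic propagation to the proximal veins, and symptomatic or fatal PE.
2. Have the existing blinded panel classify fatal PE. Data Collection lists only all-cause mortality, so cause of death must be added.
3. Report separately scan-detected DVT, propagation found on the day-14 scan, and major bleeding, with bleeding as the safety outcome.
4. Re-derive the baseline from the trauma registry if it holds symptom status and cause of death. The documents do not show that it does. Otherwise state an assumed range, or estimate the rate from the vanguard.
5. State that the existing table applies only to bleeding plus proximal DVT, and justify or drop its assumed direction.

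The cost is protocol wording, one added data item and a registry query, with no new visits or patients. The downside is a lower event rate and probably a larger definitive trial. As an assumed example for PE alone, since no PE rate is given: halving 0.5%, 1% or 2% needs about 9,383, 4,673 or 2,319 per arm (same formula, two-sided 0.05, 80% power).

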### **Purpose of the Study:**

This is a prospective, randomized vanguard trial of trauma patients admitted to the trauma surgery service at IMC who are deemed to be at high risk for venous thromboembolism (VTE). Once identified and enrolled, subjects will be randomized to receive bilateral lower extremity duplex ultrasound (DUS) surveillance (see Appendix A) versus no surveillance. We will compare the two groups with regard to deep vein thrombosis (DVT) and pulmonary embolism (PE) rates, both during the index hospitalization and at 90 days post-discharge. To our knowledge, this is the first prospective, randomized study of its kind to occur since the widespread use of low molecular weight heparins (LMWH) for VTE chemoprophylaxis in trauma patients. The results of this trial will help to assess the feasibility of performing a definitive (likely multi-institutional) trial in the

future.

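### Learning how much higher the composite rate is without surveillance is one stated reason for the vanguard, but no planned analysis estimates that difference, and 300 per arm would give only a broad range for it

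*Combined protocol and SAP*

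**What the plan says.** All the relevant text is in the protocol's Data Analysis/Statistics section, except where noted.

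- Baseline: "A historic baseline incidence of the composite outcome of major bleeding events plus proximal DVT on the trauma service is about 5.5" percent.
- Direction: "We expect that in the no surveillance group, the incidence of the composite outcome will be higher".
- Size of the difference: "We are not entirely sure how much higher, which is one of the reasons for performing this vanguard trial". The plan then says that the power table reflects this uncertainty.
- Table: rates of 6.5% to 10.0% (+1.0 to +4.5 points, in 0.5-point steps). The size per group runs from 600 at the largest difference to 4,200 at +1.5. The +1.0 row reads "Doesn't achieve 80% power at n=5000 per group".
- Size of the vanguard: "we estimate that over the course of one year, we could enroll about 300 patients per arm". The justification is feasibility: "This number of patients should be sufficient to help us determine the feasibility of a definitive, likely multi-institutional future trial". The Purpose of the Study section agrees: "The results of this trial will help to assess the feasibility of performing a definitive (likely multi-institutional) trial".
- Analysis: "A chi-squared test will be calculated to compare the rate of VTE between the surveillance group and the no surveillance group". No other analysis is named.

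The plan also says that at least 1000 per arm would be needed to discern a true difference, and that one center cannot reasonably do this definitively.

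**The concern.** The unknown size of the difference is offered as a reason for running the trial, and that difference determines which table row applies to the definitive study. The plan names no estimate of it, no confidence interval and no expected precision. The one test it names addresses VTE, not the composite on which the baseline and the table rest.

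A reader of the results would have a p-value for one endpoint and, at best, an unqualified pair of percentages for the other. The required size changes sevenfold between the +1.5 and +4.5 rows (4,200 / 600 = 7). An imprecise difference read as a firm one could therefore badly mislead the planning of the next trial.

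Feasibility, the main purpose, is not analyzed either. The Data Collection section lists variables for enrolled subjects only, so it yields no screened, eligible or opted-out counts.

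**Working it through.** **Inputs from Data Analysis/Statistics:** 5.5% baseline, taken as the surveillance-arm rate as the table does; no-surveillance rates of 6.5% to 10.0%; 300 per arm; 80% power; 3000 admissions a year, 65-75% qualifying, 50-75% agreeing. **Assumed, because not stated:** two-sided 5% level, 1:1 allocation, no losses.

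**1. The plan's table.** For two proportions with mean p̄,

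n = [1.96·√(2p̄(1−p̄)) + 0.8416·√(p1(1−p1) + p2(1−p2))]² / (p2−p1)².

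For 5.5% against 10.0%, this is (0.7412 + 0.3171)² / 0.045², giving 554 after rounding up, or 597 with a continuity correction. All rows:

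| Difference | Plan | Uncorrected | Corrected |
|---|---|---|---|
| +1.0 | over 5,000 | 8,853 | 9,052 |
| +1.5 | 4,200 | 4,087 | 4,220 |
| +2.0 | 2,500 | 2,384 | 2,483 |
| +2.5 | 1,600 | 1,580 | 1,659 |
| +3.0 | 1,200 | 1,135 | 1,201 |
| +3.5 | 900 | 861 | 917 |
| +4.0 | 700 | 680 | 729 |
| +4.5 | 600 | 554 | 597 |

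Every numeric row is within 3% of one variant, although neither variant fits all of them. The table can be taken as sound, and the assumed two-sided 5% level is consistent with it.

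**2. Precision at 300 per arm.** Half-width = 1.96·√[(0.055·0.945 + p2(1−p2)) / 300].

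- +1.0: 1.96·√(0.11275/300) = 3.80 points.
- +4.5: 1.96·√(0.141975/300) = 4.26 points.

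If the observed rates fell exactly on a row, the 95% interval would be:

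| Difference | 95% interval (points) |
|---|---|
| +1.0 | −2.80 to 4.80 |
| +1.5 | −2.37 to 5.37 |
| +2.0 | −1.94 to 5.94 |
| +2.5 | −1.51 to 6.51 |
| +3.0 | −1.08 to 7.08 |
| +3.5 | −0.64 to 7.64 |
| +4.0 | −0.20 to 8.20 |
| +4.5 | 0.24 to 8.76 |

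Each interval contains all eight rows. Newcombe intervals agree where computed, with the surveillance arm set at 5.5%: −1.6 to 6.7 at +2.5, and 0.2 to 8.9 at +4.5.

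**3. Sampling behavior, by exact binomial enumeration.** Depending on the true row, the interval covers all eight rows with probability 0.53 to 0.73. The estimate lands within 0.25 point of the true row only 6% to 13% of the time. It is zero or negative 33% of the time if the truth is +1.0, and 2% if it is +4.5.

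**4. The plan's own accrual inputs.** 3000 × 0.65 × 0.50 = 975, or about 488 per arm. 3000 × 0.75 × 0.75 = 1,687.5, or about 844 per arm. Neither matches 300 per arm, which is 600/3000 = 20% of admissions.

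- At 488 per arm the half-width is 2.98 (+1.0) to 3.34 (+4.5).
- At 844 per arm it is 2.27 to 2.54. An interval centred on +2.5 (half-width 2.39) runs from 0.11 to 4.89 and still contains every row. One centred on +1.0 reaches 1.0 + 2.27 = 3.27, so it excludes only +3.5 and above.

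**5. Size needed for real discrimination.** A half-width of 1.75 points, half the table's span, needs about 1,415 to 1,781 per arm.

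**6. Most favorable reading.** Fix the baseline at 5.5% and estimate only the no-surveillance arm. The half-width is then 1.96·√[p2(1−p2)/300] = 2.79 to 3.39 points. For example, 30/300 has an exact interval of 6.85% to 13.97%, which excludes the 6.5% row and no other.

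**The case against.** The strongest reply is that the plan already admits its limits. It asks for at least 1000 per arm for a true comparison, calls that unreasonable at one center, and justifies 300 per arm by feasibility alone. That stands as far as power goes. The plan does not, however, say that the difference will be too imprecise to choose a row, and it offers the unknown difference as a reason for the trial.

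A reader might infer several stronger points that the documents do not support:

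- **That the plan promises to show how much higher the rate is.** It calls this uncertainty one reason among several.
- **That the definitive trial will be sized from the observed difference.** No such rule is stated. The risk is that nothing warns against it.
- **That the planned test has 7% to 54% power.** Those figures hold for the composite at 300 per arm. The chi-squared test is of VTE, and the documents give no VTE rate without surveillance, so its power cannot be computed.
- **That a non-significant result would hide a benefit.** For VTE the direction is unclear. The Significance section says that about 85% of diagnosed DVTs are silent and found by surveillance, and that stopping it would lower the DVT rate.
- **That no rows can ever be separated.** The statement in step 2 is exact for intervals centred on a row. An estimate beyond the table's range could exclude rows at one end, and larger accrual or the one-arm reading can separate the extremes.

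Nor is a pooled rate from all 600 subjects a substitute. It would be more precise, but it averages arms with scheduled and symptom-triggered scanning and is not the unknown no-surveillance rate.

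**Conclusion.** The concern holds in a limited form. One stated reason for the vanguard is not served by the analysis as written: the named test is of another endpoint and estimates no difference. If the composite difference were estimated at 300 per arm, its 95% half-width would be about 3.8 to 4.3 points against a table span of 3.5. At 488 to 844 per arm it would be about 2.3 to 3.3 points against steps of 0.5. The vanguard can give a broad range for the difference but cannot choose between neighboring rows.

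This rests on the 5.5% baseline, 1:1 allocation, two-sided 95% confidence and complete follow-up; losses would widen the intervals. The widths reflect sampling error only, not the difference in detection between arms. Nothing here prevents the trial from running or from serving its feasibility purpose.

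**What to change.** In Data Analysis/Statistics:

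1. Add the composite rate in each arm and the between-arm risk difference with a 95% confidence interval, for example a score interval. The Data Collection list already includes bleeding and DVT location.
2. State the expected half-width: about 3.8 to 4.3 points at 300 per arm, revised if the target changes.
3. Say that the vanguard gives only a broad range for the difference. Add that neither the observed difference nor a non-significant p-value will by itself select a table row or decide whether the definitive trial goes ahead.
4. Keep a screening log and report screened, eligible and opted-out counts against the expected 65-75% and 50-75%. First reconcile those percentages with 300 per arm. Until then they should not serve as progression thresholds, because meeting even the lower ends at 3000 admissions gives about 488 per arm.

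The cost is a few sentences, one additional estimate and a screening log. The downside is a more modest stated aim.

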### **Hypothesis/Research Questions:**

This study will determine the rate of VTE (DVT and PE) in high-risk trauma patients who have surveillance for lower extremity DVT versus those who do not have surveillance. It will also determine the rate of DVT propagation to the popliteal vein or higher by 14 days after discharge in high-risk trauma patients found to have isolated distal DVT.

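### The only named between-arm test compares all detected VTE, but silent DVT is sought in one arm only, so the test is tilted against the plan's directional hypothesis

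*Combined protocol and SAP*

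**What the plan says.** Data Analysis/Statistics names one between-arm test: "A chi-squared test will be calculated to compare the rate of VTE between the surveillance group and the no surveillance group". The end of Methods/Procedures adds that outcome variables will be compared, without naming another test.

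The plan asks two different questions of the arms.

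- **Descriptive.** Purpose of the Study will "compare the two groups with regard to deep vein thrombosis (DVT) and pulmonary embolism (PE) rates". Hypothesis/Research Questions says "This study will determine the rate of VTE (DVT and PE) in high-risk trauma patients". Neither restricts VTE to symptomatic events.
- **Directional.** The end of Background and Significance hypothesises that patients under scheduled surveillance "will have a lower rate of symptomatic DVT, DVT propagation, and symptomatic or fatal pulmonary embolism (PE"), relative to patients without screening.

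Detection differs by design. Methods/Procedures schedules bilateral scans on days 1, 3 and 7 and then weekly in the surveillance arm; the other arm is managed "with no DUS performed unless symptomatic for DVT". Data Collection item 9 records asymptomatic DVT for the surveillance group only. Item 10 records symptomatic DVT and PE in both arms, in hospital and at 90 days.

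The Significance section recognises the mechanism. It cites a survey finding that the "VTE rate may be more a function of surveillance bias than of the quality of care", and says of the trial's own service: "If we were to discontinue routine DUS surveillance of the highest risk trauma patients, our DVT rate would certainly decrease" and "Most (approximately 85%) of the DVTs that we diagnose are clinically silent".

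**The concern.** The count entering the chi-squared test is gathered differently in the two arms. A silent clot is recorded if the patient was allocated to scanning, and otherwise only if it later causes symptoms and is imaged. Blinded adjudication makes classification even-handed but cannot supply clots that were never imaged.

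Read as a test of the directional hypothesis, the comparison starts from more recorded VTE with surveillance, whatever surveillance does to symptomatic events. A real benefit could be hidden or appear reversed. The results are meant to inform a definitive trial, so a significant difference produced by scanning could be carried forward as evidence of harm, or as an effect size for planning.

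**Working it through.** **The plan's own figures.** The planning table concerns another outcome: major bleeding plus proximal DVT, 5.5% baseline. It is still useful for judging which chi-squared version is meant. Two-sided 5% is assumed, because no significance level is stated, with 80% power:

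n = [1.96·√(2p̄(1−p̄)) + 0.84·√(p₁(1−p₁)+p₂(1−p₂))]² / (p₂−p₁)²

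For 7.0% to 10.0% in half-point steps this gives 4,087, 2,384, 1,580, 1,135, 861, 680 and 554. With continuity correction it gives 4,220, 2,483, 1,659, 1,201, 917, 729 and 597. The table states 4,200, 2,500, 1,600, 1,200, 900, 700 and 600. Five of the seven rows are nearer the corrected formula, but neither version fits all of them. Ranges below therefore run from corrected to uncorrected.

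**Inputs.** 300 per arm (Data Analysis/Statistics); 3% DVT and 85% silent (Significance). The last two are service figures under partial scanning: Background and Significance says that only high-risk patients who cannot receive enoxaparin are routinely scanned. Using them for a fully scanned arm is an assumption, as are all PE, detection and conversion rates. Conversion means the share c of unscanned silent DVT that later surfaces and is counted. DVT and PE are added, ignoring overlap.

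**Recorded rates with no true effect.**

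- Surveillance arm, full detection: 3.0%.
- No-surveillance arm: 3% × 0.15 + c × (3% × 0.85) = 0.45% + c × 2.55%.

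The probability of rejection is exact: the product of two binomial probabilities, summed over all tables where the test rejects and surveillance is higher.

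| Assumptions | Surveillance vs none | Significantly more VTE with surveillance |
|---|---|---|
| Equal recorded rates (reference) | 3.0% vs 3.0% | 1.4–2.5% |
| c = 0 | 3.0% vs 0.45% | 59–71% |
| c = 25% | 3.0% vs 1.09% | 27–39% |
| c = 50% | 3.0% vs 1.73% | 11–18% |
| c = 75% | 3.0% vs 2.36% | 4–7% |
| 1% PE in both arms, c = 0 | 4.0% vs 1.45% | 39–50% |
| 1% PE, 80% detection of silent DVT, c = 25% | 3.49% vs 2.09% | 12–18% |

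In the last row, 0.45% + 0.8 × 2.55% + 1% = 3.49%. If missed silent clots in the surveillance arm also convert, that rate is 3.62% and the result is 14–20%. At c = 0 the figure is 33–52% with 2% DVT and 87–92% with 5%.

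**If surveillance works.** Suppose it halves a 1% PE rate. A clot found on a scan stays in the count even if its symptoms are averted, so surveillance records 3.0% + 0.5% = 3.5%. The other arm records 1.45% + c × 2.55%.

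| c | Surveillance vs none | Significantly more VTE with surveillance | Significantly less |
|---|---|---|---|
| 0 | 3.5% vs 1.45% | 27–37% | below 0.1% |
| 25% | 3.5% vs 2.09% | 12–18% | 0.1% |
| 50% | 3.5% vs 2.73% | 5–8% | 0.3–0.6% |

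The recorded rates become equal at c = (3.5 − 1.45)/2.55 = 80%. Below that, the recorded difference points against surveillance even though it works.

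**The case against.** The strongest reply is that the test does what two sections ask. Purpose of the Study and Hypothesis/Research Questions want detected rates under the two policies, and an unrestricted comparison gives them. This stands. With equal recorded rates of 3%, the total two-sided rejection rate is 2.7–5.1%, so the test is sound for detected rates. A reader might infer that it is simply invalid; the documents do not support that. The defect is that the hypothesis asks something else and the analysis section does not assign the test.

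Second, the data already separate silent from symptomatic events (items 9 and 10), and the authors know about surveillance bias. That also stands and makes the repair cheap, but no sentence names the symptomatic comparison.

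Third, the trial is for feasibility, and no decision or stopping rule rests on this test. This lowers the severity.

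Two stronger readings of the size are tempting. One is that most such trials would show spurious harm. That needs full detection, no PE and no silent clot surfacing by day 90; the combined case gives 12–18%. The other is that a result favouring surveillance is all but impossible. Its chance is below 1% in the benefit cases shown, but it rises with conversion.

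A reader might also set the expected rise in the composite without surveillance against the predicted fall in DVT if scanning stopped, and call that a contradiction. The first concerns bleeding plus proximal DVT, the second all DVT, so the two statements need not conflict.

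**Conclusion.** The concern holds in this form: the one named between-arm test answers the descriptive question, is tilted against the directional hypothesis, and is not assigned to either. With no true effect, the chance of significantly more VTE with surveillance ranges from 4–7% to 59–71% as conversion falls from 75% to none, against 1.4–2.5% under equal detection. The tilt disappears only as conversion approaches 100%.

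The direction follows from the design. The size rests on service figures from a partly scanned population and on assumed PE, detection and conversion rates, so no single percentage should be quoted as the bias. The point should be fixed before analysis; given the feasibility purpose, it is not a must-fix.

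**What to change.** In Data Analysis/Statistics:

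- Name the comparison that serves the directional hypothesis: adjudicated, objectively confirmed symptomatic DVT, or symptomatic or fatal PE, to day 90 (item 10). Report a risk difference with a score or exact 95% CI.
- Apply one counting rule in both arms: attributable symptoms or signs documented, and the event confirmed on adjudicated imaging. A DVT first seen on a scheduled scan counts if such symptoms were documented before the scan or later. Counting only symptoms before the scan would create the reverse bias: with 25% conversion and the same true course, 0.45% vs 1.09%, instead of 1.09% in both arms.
- Have the blinded adjudicators use the same symptom criteria throughout. Show results with and without the scan-first cases, because a known clot may make attribution of later symptoms easier.
- Keep total VTE, labelled as a detected rate that depends on scanning and not as a test of the hypothesis. If the chi-squared test is kept, say whether it is continuity-corrected.
- Report asymptomatic DVT (item 9) as screening yield and propagation (item 11) descriptively, since finding either depends on scanning.

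The cost is wording plus one data field, the date of first symptoms or signs for each DVT. The daily targeted examinations can supply it in hospital; after discharge it depends on record review and may be missing.

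The price is precision. Expected events per arm are 300 × 0.45% = 1.35, or 300 × 1.09% ≈ 3.3 with 25% conversion, or 300 × 1.45% = 4.35 with 1% PE and no conversion. The score 95% CI for the risk difference is about ±1.6 points at 1 vs 1 events and ±2.2 points at 4 vs 4. Some ascertainment difference will remain because the treating clinicians are not blinded, and the plan should say so.
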